14. MONITORING THE STUDY

Monitoring will be conducted by the Sponsor and/or a contract research organization according to standard operating procedures. Site visits will be conducted by the Sponsor or their representatives at regular intervals to conduct inspections.

A full description of the monitoring procedures for this study will be detailed in the Clinical Monitoring Plan.

The Investigator will grant representatives of the Sponsor's clinical operations team and quality team, as well as regulatory agencies and ethical committees access to inspect facilities and records (including subject charts) relevant to this study and agrees to assist the monitors in their activities, if requested.

An Independent Data Monitoring Committee (IDMC) will be organized for this study. A full description of the IDMC procedures for this study will be detailed in the Medical Monitoring (Safety) Plan and IDMC Charter. The IDMC will closely monitor the incidence of diarrhea as it could potentially be a vehicle for the spread of SARS-CoV-2. Enrollment will be paused while the IDMC conducts its first interim analysis of safety and futility. The IDMC may also conduct analyses of safety, futility and effectiveness if the number of COVID-19 illnesses is higher than anticipated.

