### 2.2 Analysis Populations

#### 2.2.1 Population Definitions

Subjects will be considered enrolled in the study upon completion of the baseline procedures. The following analysis populations will be used in the study.

- **Safety Population** – the safety population includes all patients who are enrolled in the study and that have received at least one dose of the assigned treatment arm (NTZ or placebo)
- **Intention to Treat Population (ITT)** – the ITT population includes all patients in the safety population who did not have a laboratory detected respiratory virus infection at the baseline visit.

The safety population will be used for all safety analyses. The ITT population will be the primary population for all efficacy analyses.

Data listings displaying the patients excluded from each population will be created. These listings will be relative to all patients enrolled in the study.

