## 2.4 Interim Analyses

A first review for safety will be conducted by the Independent Data Monitoring Committee (IDMC) when 20% of the planned number of subjects have completed three weeks of treatment. This review will examine the available data for safety signals contained in the AE, vital sign, and clinical laboratory data.

An unblinded analysis may be performed under circumstances defined in the IDMC charter, which relate to the rate of COVID-19 illnesses and the rate of occurrence of diarrhea as an adverse event.

If conditions required for unblinding are satisfied, futility will be assessed using a conditional power approach assessing the efficacy of NTZ for the COVID-19 endpoint. The IDMC will recommend stopping for futility if the conditional power of the study at that stage is less than 30%. The conditional power will be calculated according to Chow and Chang (2007):

$$\text{Conditional Power} = 1 - \Phi \left( \sqrt{z_{1-\alpha_2}^2 - z_{1-p_1}^2} - \frac{\delta}{\sigma} \sqrt{n_2} \right).$$

In the above,  $z_{\alpha}$  refers to the  $\alpha$ -th quantile of the Standard Normal distribution,  $\alpha_2$  is the planned final significance level of the study,  $p_1 > \alpha_2$  is the  $p$ -value at the first interim analysis,  $\delta$  is the observed study effect size (i.e., the difference in observed rates in the two groups),  $\sigma$  is the observed standard error of the difference in rates at the interim, and  $n_2$  is the number of subjects remaining to be enrolled in the study.

A second review for safety and futility will be conducted by the IDMC when 50% of the planned number of subjects have completed 6 weeks of treatment. An unblinded analysis will be conducted under circumstances defined in the IDMC charter, which relate to the rate of COVID-19 illnesses, the rate of occurrence of diarrhea as an adverse event and other safety considerations. Futility will be concluded if the CMH test statistic for comparing the treatment groups on the COVID-19 endpoint is less than 0.179 (i.e., a  $p$ -value greater than 0.3278). This bound was set using O'Brien-Fleming bounds for futility with overall  $\alpha = 0.049$ .

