## 4.2 Efficacy Analysis

### 4.2.1 Primary Efficacy Variables

The study has two primary efficacy endpoints: reduction in symptomatic COVID-19 disease and reduction in all VRI. The study-wise  $\alpha$  level is set at 0.05, allocated with 0.049 to the COVID-19 endpoint and 0.001 to the all VRI endpoint. See Section 2.4 for details on how the study- wise  $\alpha$  level will be allocated to the interim and final analyses. For each endpoint, the following hypotheses will be tested

$$H_0: p_1 = p_2$$

$$H_1: p_1 \neq p_2,$$

here,  $p_1$  represents the probability of symptomatic disease (either COVID-19 or VRI) in the NTZ treatment group and  $p_2$  represents the probability of symptomatic disease in the placebo group.

The proportion of subjects experiencing symptomatic COVID-19 disease in the NTZ treatment group will be compared to the similar proportion in the placebo group using a two-sided CMH test with continuity correction at  $\alpha=0.047$ . The test will be stratified by LTCF. The contingency tables will be provided with rates relative to the treatment margins. A 95% confidence interval for the odds ratio of symptomatic COVID-19 infection in the NTZ group relative to the placebo group will be provided. The risk difference for the treatment groups and a 95% confidence interval for the difference will be provided.

The proportion of subjects experiencing symptomatic VRI infections in the NTZ treatment group will be compared to the similar proportion in the placebo group using a two-sided CMH test, stratified by LTCF with continuity correction at  $\alpha=0.001$ . The contingency tables will be provided with rates relative to the treatment margins. A 95% confidence interval for the odds ratio of symptomatic VRI in the NTZ group relative to the placebo group will be provided. The risk difference for the treatment groups and a 95% confidence interval for the difference will be provided.

CMH analyses of symptomatic COVID-19 disease and symptomatic VRI will be repeated with subjects divided by sex (female or male), age (65- to 79 years or 80 years and over), and race (white or non-white). Estimates and confidence intervals for the odds ratio and relative risk differences will be provided.

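### The conditional-power formula in SAP 2.4 counts sample size twice, so its drift is too large by √n1 (12.6 if 160 subjects are analysed); the effect on the futility recommendation depends on a p-value the SAP does not define

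*SAP*

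**What the plan says.** SAP 2.4 places the first review at the point when "20% of the planned number of subjects have completed three weeks of treatment". If charter conditions for unblinding are met, futility on the COVID-19 endpoint is judged by conditional power:

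CP = 1 − Φ( √(z²(1−α2) − z²(1−p1)) − (δ/σ)·√n2 ).

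The SAP defines δ as "the difference in observed rates in the two groups", says that σ "is the observed standard error of the difference in rates at the interim", and says that n2 "is the number of subjects remaining to be enrolled in the study". The decision rule reads "The IDMC will recommend stopping for futility if the conditional power of the study at that stage is less than 30" per cent.

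SAP 2.4 describes this look as a review for safety. Protocol section 14 says "Enrollment will be paused while the IDMC conducts its first interim analysis of safety and futility". The SAP does not say whether p1 is one- or two-sided or continuity-corrected, which direction δ takes, or whether α2 is halved. SAP 4.2.1 specifies a "two-sided CMH test with continuity correction" for the final COVID-19 comparison.

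**The concern.** With σ defined as a standard error, δ/σ is already the interim z statistic. Projecting it onto the remaining subjects needs the ratio of stage sizes, √(n2/n1). Multiplying by √n2 instead uses the interim sample size once inside σ and then fails to take it out again.

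The drift becomes so large in absolute size that it swamps the other term. Any visible NTZ lead pushes the result towards 100% and any deficit towards 0%. A committee given such a figure would not be seeing a conditional power, and the 30% threshold would lose its meaning. The cost would be efficiency and continued exposure of residents in a trial with little prospect of success.

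**Working it through.** **The SAP's own nearest figure.** The SAP prints no worked conditional power. The closest figure built from the same quantities is the 87.1% final power in SAP 1.3 (5% against 1%, 400 per arm, two-sided alpha 0.047). Null SE = √(0.03·0.97·2/400) = 0.01206. Alternative SE = √((0.0475+0.0099)/400) = 0.01198. With continuity correction 1/400: Φ((0.04 − 0.0025 − 1.986·0.01206)/0.01198) = Φ(1.13) = 87.1%. It reproduces.

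**The scaling factor.** Let s be the per-subject SD, with 1:1 allocation and n1, n2 as totals. The interim SE is 2s/√n1 and the second-stage SE is 2s/√n2.
- Coherent drift: δ/(2s/√n2) = (δ/σ)·√(n2/n1).
- Printed drift: (δ/σ)·√n2.
- Ratio: √n1, whatever the rates or n2.

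With n1 = 20% of 800 = 160 and n2 = 640, at 5% against 1%: σ = √((0.0475+0.0099)/80) = 0.02679 and δ/σ = 1.493. The printed drift is 1.493·√640 = 37.8. The coherent drift is 1.493·√4 = 2.99. The ratio is 12.65 = √160. A simulated second stage of 320 per arm had a mean z of 2.98, matching the coherent value.

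**Single looks.** Assumptions: 80 per arm, 640 remaining, α2 = 0.047, δ = placebo minus NTZ, one unstratified table. For 3 NTZ against 4 placebo cases, σ = 0.03233 and δ/σ = 0.387, so the drift is 9.78 as printed and 0.773 corrected.
- Two-sided uncorrected p1 = 0.700: root = √(1.675² − 0.524²) = 1.590. CP = 1 − Φ(1.590 − 9.78), above 99.9%; corrected, 1 − Φ(1.590 − 0.773) = 21%.
- One-sided p1 = 0.350: root = √(1.675² − 0.385²) = 1.630. Above 99.9%; corrected, 20%.
- Two-sided continuity-corrected: the statistic is 0, p1 = 1, z(1−p1) is infinite, and there is no value.

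| NTZ vs placebo cases | As written (uncorrected p1) | Scaling corrected, one-sided / two-sided p1 | Continuity-corrected p1 |
|---|---|---|---|
| 3 vs 4 | >99.9% | 20% / 21% | no value |
| 4 vs 5 | >99.9% | 17% / 19% | no value |
| 1 vs 2 | about 100% | 34% / 31% | no value |
| 4 vs 3 | about 0% | about 1% | no value |

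The sign-check behaviour is not exact when the arms differ in size: with one-sided p1, 4/80 against 4/76 reads 58% as written.

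**How often the rule fires.** Exact binomial enumeration, changing only √n2 to √(n2/n1). Firing means CP below 30%; looks with p1 ≤ α2 are not counted as firing.

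| Scenario | Two-sided uncorrected | One-sided | Two-sided continuity-corrected |
|---|---|---|---|
| n1=160, 3% in both arms | 38% → 48% | 54% → 63% | 23% → 23% (53% of looks have no value) |
| n1=160, 1.5% in both arms | 35% → 37% | 51% → 53% | 15% → 15% (70% have no value) |
| n1=120, 3% in both arms | 37% → 43% | 54% → 55% | 20% → 20% |
| n1=240, 3% in both arms | 40% → 59% | 53% → 69% | 27% → 30% |
| n1=160, NTZ 1%, placebo 5% | 3% → 7% | 9% → 12% | 0.8% → 0.8% |

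The 1.5% row assumes that half of the six-week risk has accrued by a three-week look. With α2 = 0.049, the one-sided entry in the first row becomes 53% → 62%; the other two entries in that row do not change.

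**The case against.** The strongest reply concerns consequence, not algebra. A reader might infer that the committee would see a figure near 100% at any small NTZ lead and that correcting the scaling would reverse the recommendation. The documents do not support that as a general statement.
- The only COVID-19 test the SAP names is continuity-corrected. Under it, a one-case difference has no value, and at n1 = 160 firing is the same before and after. The larger difficulty on that reading is the share of looks with no value.
- The look is triggered by three weeks of treatment. At 1.5% per arm, about 2.4 cases (160 × 0.015) are expected in total, so a seven-case split is not typical. For 1 against 2 cases the corrected value stays above 30%. Some subjects will have been followed for longer, so the truth may lie between the 1.5% and 3% scenarios.
- Use is contingent on charter conditions that are not shown, stopping is a recommendation, and SAP 2.4 has a separate futility rule at 50%.
- The formula is attributed to a textbook that was not available here, so what would actually be programmed is unknown.

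All of this stands as a limit on size. None of it removes the error: the symbols are defined explicitly, nothing else in either document rescales σ, and anyone following the definitions would compute the wrong drift. It would also be wrong to infer inflated type I error, since the formula can only recommend stopping for futility, and the error leans towards continuing.

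**Conclusion.** The formula is wrong as written and should be fixed. The √n1 overstatement is exact under 1:1 allocation with total counts. The value 12.6 rests on 160 analysed, and n1 may differ: the efficacy population keeps only those who "did not have a laboratory detected respiratory virus infection at the baseline visit", while more than 160 may have been randomized by that date.

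The effect on the recommendation is real but conditional. At n1 = 160 with no effect, correcting the scaling adds 0 to about 9 points of futility firing at 3% per arm and 0 to about 2 points at 1.5%. The added looks are those with NTZ ahead. At n1 = 240 and 3% per arm the shift runs from about 2 to 19 points. Zero is the result at n1 = 160 under the continuity-corrected p1; the upper ends need an uncorrected p1. These figures assume an unstratified table, α2 = 0.047 and δ taken as placebo minus NTZ.

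**What to change.** Keep σ as the standard error and replace √n2 with √(n2/n1), where n1 is the number analysed at the interim. Equivalently, define σ as the per-subject SD and use √n2/2 for two equal arms. The half matters: at 5% against 1%, the per-subject SD with √640 alone gives a drift of 5.97, still twice the coherent 2.99. Match the IDMC charter if it repeats the formula.

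This changes one factor and its symbol definitions, with no effect on conduct, data collection or the final test. The price is somewhat more futility firing at the planned 5% against 1%: 3% to 7% with a two-sided uncorrected p1, 9% to 12% one-sided, and no change at n1 = 160 with the continuity-corrected p1.

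Separately, and not as part of this correction, the sponsor should state the direction of δ, the sidedness and continuity correction of p1, which α2 enters, and what is reported when the formula has no value. These are design choices on which statisticians may differ. If α2 is halved, the 30% threshold should be reconfirmed. All of this should be settled before any unblinded look, so that it cannot appear to be driven by the data.

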## Abbreviations and acronyms

---

AE	Adverse Event
ARI	Acute Respiratory Illness
ATC	Anatomic Therapeutic Chemical
CDER	Center for Drug Evaluation and Research
COVID-19	Novel Corona Virus Infectious Disease, 2019
CMH	Cochran-Mantel-Haenszel Chi-square Test
FDA	US Food and Drug Administration
IAP	Interim Analysis Plan
LTCF	Long Term Care Facility
NTZ	Nitazoxanide
RT-PCR	Reverse Transcriptase-Polymerase Chain Reaction
SARS-CoV-2	Severe Acute Respiratory Syndrome-Corona Virus 2, the pathogen causing COVID-19
TEAE	Treatment Emergent Adverse Event
VRI	Viral Respiratory Illness
WHO	World Health Organization

---

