### 1.3 Sample Size

Recent reports of COVID-19 in long-term care facilities in the United States have suggested a high rate of transmission of the SARS-CoV-2 virus, but infection control procedures may significantly decrease transmission (McMichael et al. 2020, Kimball et al. 2020). A recent study of 264 elderly volunteers ( $\geq 65$  years of age) reported 1.6 respiratory tract infections (not laboratory-confirmed) per person-year indicating approximately a 20% probability of respiratory tract infection over a given 6-week period (Mannick et. al, 2018). Infection control procedures in place during the period covered by this clinical trial are also expected to reduce the transmission of other respiratory viruses.

For purposes of calculating sample size, we assume that the proportion of subjects experiencing COVID-19 over a 6-week period is 5%, the proportion of subjects experiencing any VRI is 10%, and that effective prophylaxis will reduce the rate of COVID-19 and other VRIs by 80%.

A Cochran-Mantel-Haenszel (CMH) chi-square test stratifying by 20 LTCFs will have 87.1% statistical power to detect the difference between 5% and 1% rates of occurrence of COVID-19 across all strata at a two-sided alpha of 0.047 with a total sample size of 800, allocated equally to strata (LTCFs) and treatment groups within strata. The statistical

power remains >87% when the number of LTCFs is 5, 10, 16 or 20. The CMH chi-square test has 91% power to detect the difference between 10% and 2% rates of occurrence of VRIs over all strata at a two-sided alpha of 0.001 with 800 subjects allocated equally to 20 LTCFs. Both tests are insensitive to stratum size. Varying the number of subjects per stratum (LTCF) between a minimum of 8 to a maximum of 80 while holding both the effect size and total sample constant results in changes in the third significant figure of the test's power.

A sample size of 800 subjects (400 per treatment group) was selected.

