An interim analysis of effectiveness will be performed when there are at least 25 laboratory-confirmed COVID-19 cases observed among the study participants. If the assumptions made in the power calculations are correct (COVID-19 rate is 0.05 in the placebo group and 0.01 in the NTZ group) we expect to observe only 24 events during the entire study. If this milestone is reached early, it indicates that the assumptions were

conservative and merit review given the high rate of mortality observed from COVID-19 illness in this population. This review will be conducted by the IDMC in accordance with its charter and will encompass both a safety and efficacy determination. In the event that the timing of the interim analysis of effectiveness is near that of the second review for safety and futility, analyses of safety, futility and effectiveness may be performed simultaneously.

O'Brien-Fleming bounds are used to set the Type I error rates for the third interim and final analyses. The interim efficacy review will be performed with  $\alpha = 0.0052$  (overall), allocated 0.005 to the COVID-19 endpoint and 0.0002 to the VRI endpoint. The final data analysis (if the efficacy hypotheses are not rejected at the interim review) will be performed with  $\alpha = 0.048$ , allocated 0.047 to the COVID-19 endpoint and 0.001 to the VRI endpoint. Power at the interim analysis is 31% for the COVID-19 endpoint. If the interim review for efficacy does not occur (i.e., the event count of 25 is not reached or reached too late in the study for the interim review to be useful), the alpha levels for the final analysis will be 0.049 for the COVID-19 endpoint and 0.001 for the VRI endpoint.

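### The 50% futility bound in SAP 2.4 is two different rules: a CMH statistic of 0.179 has two-sided p = 0.672, not 0.3278

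*SAP*

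**What the plan says.** SAP section 2.4 plans a second IDMC review for safety and futility once half of the planned subjects have completed six weeks of treatment. Unblinding at that review is conditional: "An unblinded analysis will be conducted under circumstances defined in the IDMC charter". The decision rule reads: "Futility will be concluded if the CMH test statistic for comparing the treatment groups on the COVID-19 endpoint is less than 0.179". A parenthesis then offers, as an equivalent, a p-"value greater than 0.3278". On the origin of the bound the SAP says "This bound was set using O'Brien-Fleming bounds for futility with overall" alpha of 0.049. It gives no beta or power for the bound, and it does not say whether the p-value is one- or two-sided.

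The scale of the statistic is set elsewhere. The SAP's abbreviation list expands CMH as "Cochran-Mantel-Haenszel Chi-square Test". Section 4.2.1 specifies the COVID-19 comparison as a "two-sided CMH test with continuity correction at" the stated alpha. Protocol section 8.4.1 also calls it a two-sided CMH chi-square test. The bound is not restated anywhere else; protocol section 14 mentions futility only in general terms.

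**The concern.** The sentence presents the two thresholds as one rule in two notations. If they are not equivalent, the plan holds two futility rules for a primary endpoint, and some results will be futile under one and not under the other. An IDMC looking at unblinded data would then have to choose which half to follow. Pre-specification is meant to remove that choice.

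**Working it through.** **Inputs.** Bound 0.179 and p-value 0.3278 (SAP 2.4). Two-sided chi-square CMH test (SAP abbreviations and 4.2.1; protocol 8.4.1). The degrees of freedom are not printed, but two arms and a binary outcome give 1 df. Planned rates are 5% placebo and 1% NTZ, with 800 subjects (SAP 1.3), so about 200 per arm at the look.

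**Reproducing 0.3278.** For 1 df, P(χ² ≤ x) = 2Φ(√x) − 1. With √0.179 = 0.42308 and Φ(0.42308) = 0.66388, this gives 0.32777. The printed figure is therefore the lower tail. Rounding of the bound is compatible with this: 0.1785 to 0.1795 gives lower tails of 0.3273 to 0.3282.

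**The p-value at 0.179.** P(χ² > 0.179) = 2 × (1 − 0.66388) = 0.672.

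**The statistic at p = 0.3278.** z = Φ⁻¹(1 − 0.3278/2) = 0.9786, and z² = 0.958.

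**Other readings.**
- 0.3278 as a one-sided p: z = 0.446 and z² = 0.199, which is close to 0.179 but not equal.
- One-sided p from √0.179: 0.336. Rounding of the bound gives 0.3359 to 0.3363, which excludes 0.3278.
- 0.179 as a z value: p = 0.429 one-sided or 0.858 two-sided.

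None of these makes the pair agree.

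**Chance of concluding futility, given that the look is unblinded.** These are simulations of 400,000 trials per scenario, with 20 LTCFs and 10 subjects per arm in each at the look. LTCF sizes and rates are equal and there are no missing data. The 20% conditional-power look and the 25-case efficacy look are ignored. The second and third scenarios are assumptions chosen for illustration. Uncorrected figures are in brackets.

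| NTZ vs placebo | CMH < 0.179 | two-sided p > 0.3278 |
|---|---|---|
| 1% vs 5% (planned) | 4.4% (1.8%) | 11.9% (5.9%) |
| 2% vs 5% | 15.9% (8.7%) | 33.8% (23.4%) |
| 3% vs 3% | 53.9% (33.4%) | 80.0% (65.9%) |

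Exact enumeration in a single stratum gives 4.3% and 11.9% for the planned rates (1.8% and 5.8% uncorrected). SAP 1.3 says "power remains >87% when the number of LTCFs is 5, 10, 16 or 20"; repeating the simulation with 5 or 10 LTCFs moves the results by at most 0.2 points. With assumed heterogeneity between LTCFs (gamma multiplier, mean 1, variance 1), the planned case becomes 5.1% and 12.8% (2.0% and 6.3%).

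**Power if the rule is binding, final alpha 0.049.** Corrected: 90.2% without the rule, 88.4% with the statistic form, 83.5% with the p-value form. Uncorrected: 94.2%, 93.3% and 90.7%. At alpha 0.047 the values are up to 0.3 points lower.

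**Worked tables, 200 per arm in one stratum.** With m cases in total, the variance is 0.25 × m × (400 − m)/399, and the corrected statistic is (|a − m/2| − 0.5)² divided by that variance, where a is the NTZ count. Under the planned rates "we expect to observe only 24 events during the entire study", so about 12 half-way.
- 4 vs 7: variance 2.681. Corrected 1²/2.681 = 0.37; uncorrected 1.5²/2.681 = 0.84. The two forms conflict either way.
- 4 vs 8: variance 2.917. Corrected 1.5²/2.917 = 0.77, a conflict; uncorrected 2²/2.917 = 1.37, no conflict.
- 2 vs 10, the split expected under the planned rates: 4.20 corrected, 5.48 uncorrected, no conflict.

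**The case against.** The arithmetic is not in dispute; the objections concern how much it matters.

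First, the rule operates only if the charter's conditions for unblinding are met. The charter is not among the documents and may state the bound correctly. This stands: every probability above is conditional on unblinding. A correct charter would still leave the SAP sentence inconsistent.

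Second, section 2.4 does not say that the futility p-value is two-sided. If it is one-sided, the cut-offs are 0.179 and 0.199, and the practical gap almost vanishes: 4.4% under both in the planned case, 53.9% versus 54.0% at 3% in both arms, and 46.0% versus 48.7% at 5% in both arms (corrected). The size of the problem therefore depends on the reading. The one-sided reading still does not reconcile the two figures, it departs from the two-sided test that both documents specify, and it leaves the lower-tail match at 0.179 unexplained.

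Third, under the planned effect the cost is moderate. If the rule is binding, the two forms differ in power by 4.9 points corrected (88.4 − 83.5) or 2.6 uncorrected (93.3 − 90.7), and the most likely results at the planned rates do not fall in the disputed zone. This also stands. The simulated power without the rule is above the SAP's stated 87.1%, so the differences between forms are a better guide than the absolute levels.

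**Conclusion.** The concern holds. The two halves of the futility rule are not equivalent on any reading tried. On the two-sided 1-df test that the documents define, every statistic from 0.179 up to 0.958 receives opposite answers. Under the planned effect the p-value form concludes futility about 2.7 times as often as the statistic form with the continuity correction (11.9/4.4), and about 3.3 times as often without it (5.9/1.8). With no effect at 3% in both arms the gap is 26.1 points corrected or 32.5 uncorrected. These sizes assume that the look is unblinded, that 0.3278 is a two-sided p-value, and that there are 200 subjects per arm in equal-sized LTCFs. Type I error is not inflated.

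The lower-tail match suggests that 0.179 was the starting figure and the p-value is the wrong half, but the documents do not prove it. As a side check, O'Brien-Fleming-type beta spending at half the information, with two-sided alpha 0.049 and an assumed power of 85%, gives squared-z bounds of 0.174 to 0.187. Assumed powers from 80% to 92.8% give about 0.32 down to 0.02. The SAP does not state the beta used, so only the original calculation can settle the matter.

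This must be fixed because a pre-specified stopping rule on a primary endpoint gives two answers on plausible data. The simulated sizes are secondary to that.

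**What to change.** Before the 50% look, check both figures against the original O'Brien-Fleming calculation. State a single bound with the p-value that belongs to it, and say whether that p-value is one- or two-sided. If the chi-square bound of 0.179 is what the calculation gave, the matching text is a two-sided p above 0.672. State the bound on the same statistic, continuity-corrected or not, that was used to derive it. If the IDMC charter repeats the bound, bring it into line. The choice of bound is the sponsor's.

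The cost is one lookup and one corrected SAP sentence, plus the charter if needed, with no extra subjects or data. It should be settled before anyone sees unblinded results, because a futility rule chosen afterwards is no longer pre-specified.

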8.4.1. Efficacy Analyses

Efficacy analyses will be based on a population consisting of all subjects randomized without a laboratory-detected viral respiratory infection at the baseline visit (intention-to-treat or ITT population).

There will be two primary efficacy analyses:

- The proportion of subjects experiencing COVID-19 in the NTZ treatment group will be compared to that of the placebo treatment group using a two-sided Cochran-Mantel-Haenszel (CMH) chi-square test ($\alpha = 0.049$).
- The proportion of subjects experiencing VRI in the NTZ treatment group will be compared to that of the placebo treatment group using a two-sided CMH chi-square test ($\alpha = 0.001$).

Secondary analyses will be performed as follows:

- Proportions of subjects experiencing hospitalization due to COVID-19 or complications thereof will be compared by treatment group using a two-sided CMH Chi-square test (unadjusted $\alpha = 0.05$).
- Proportions of subjects experiencing mortality due to COVID-19 or complications thereof will be compared by treatment group using a two-sided CMH Chi-square test (unadjusted $\alpha = 0.05$).
- Proportions of subjects (with or without symptoms) testing positive for antibodies to SARS-CoV-2 at either of the Week 6 or Week 8 visits will be compared by treatment group using a two-sided CMH Chi-square test (unadjusted $\alpha = 0.05$).

Exploratory analyses will be performed as follows:

- Proportions of subjects experiencing each of the following will be compared by treatment group using a two-sided CMH Chi-square test (unadjusted $\alpha = 0.05$): (i) hospitalization due to VRI or complications thereof; (ii) mortality due to VRI or complications thereof, (iii) acute respiratory illness (ARI), (vi) hospitalization due to ARI or complications thereof; and (v) mortality due to ARI or complications thereof.

Other analyses may be performed as outlined in the study Statistical Analysis Plan.

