10. ADVERSE EVENTS

The term “adverse event” is defined for purposes of this study as any unwanted physical, psychological or behavioral change experienced by a subject during the course of the study and after taking the first dose of study medication regardless of its severity or relation to the study. Adverse events may include symptoms, signs, unexpected worsening of pre-existing conditions, clinically significant changes in laboratory values, diseases and syndromes, and significant and unexpected failures of pharmacological action of other medications. Symptoms of VRIs (cough, sore throat, nasal obstruction, fatigue, headache, myalgia, feverishness) and complications of VRIs will not be reported as adverse events.

Adverse events will be recorded on the appropriate EDC forms throughout the study, and the severity of each adverse event will be graded on a four-point scale: mild, moderate, severe, or life-threatening (See [Appendix II](#)). The duration of the adverse event and relationship to the study drug will also be recorded. All adverse events must be followed until their resolution or stabilization even beyond the planned study period.

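### The 50% futility rule uses an unsigned CMH chi-square, so it is met most often when the arms are equal and less often as NTZ does worse than placebo

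*SAP*

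**What the plan says.** SAP section 2.4 plans a second IDMC review, for safety and futility, when half the planned subjects have completed six weeks of treatment. The unblinded analysis depends on conditions in the IDMC charter. The rule reads: "Futility will be concluded if the CMH test statistic for comparing the treatment groups on the COVID-19 endpoint is less than 0.179". It adds in brackets that this means a p-"value greater than 0.3278". On the origin of the bound it says "This bound was set using O'Brien-Fleming bounds for futility with overall" alpha of 0.049.

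The SAP's abbreviation list expands CMH as "Cochran-Mantel-Haenszel Chi-square Test". SAP section 4.2.1 compares the arms "using a two-sided CMH test with continuity correction", stratified by LTCF, against the alternative that the two probabilities differ. Protocol section 8.4.1 also tests COVID-19 "using a two-sided Cochran-Mantel-Haenszel (CMH) chi-square test". Neither document gives the futility statistic a sign or says that the difference must favour NTZ.

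**The concern.** Futility should be declared when the trial is unlikely to show that NTZ prevents COVID-19. That includes data showing no difference and data running the wrong way. A rule that stops for a small chi-square covers only the first case. Once NTZ has clearly more cases than placebo, the statistic rises above the bound and the criterion is not met, although a positive result has become less likely. The rule also passes about half of the null trials that happen to lean towards placebo. At stake is continued enrolment of LTCF residents into a trial that has little chance of showing benefit.

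**Working it through.** **Inputs.** Total 800, allocated 1:1 (SAP 1.3), so the 50% look has 400 subjects, taken as 200 per arm. COVID-19 rates of 5% on placebo and 1% on NTZ (SAP 1.3 and 2.4). Continuity-corrected CMH (SAP 4.2.1). NTZ rates of 7.5%, 10% and 15% are assumptions chosen to show the pattern.

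**Step 1: which scale is 0.179 on?** For a chi-square with 1 df, P(X < 0.179) = 0.3278 and P(X > 0.179) = 0.6722. The SAP's 0.3278 is therefore the lower-tail probability at 0.179. Other readings do not fit:
- 0.179 as a Z-score gives p = 0.429 (one-sided) or 0.858 (two-sided).
- p = 0.3278 two-sided needs chi-square 0.958.
- p = 0.3278 one-sided needs Z = 0.446, whose square is 0.199.

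So 0.179 is on the unsigned chi-square scale, and the printed p-value is the complement of the correct one.

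**Step 2: two examples.** For a single table with m total cases, n = 200 per arm and N = 400, the statistic is (|NTZ cases − m/2| − 0.5)² / V, with V = n·n·m·(N − m) / [N²(N − 1)].
- 10 NTZ and 10 placebo cases: the difference from expectation is 0, the statistic is 0, and futility is declared.
- 20 NTZ and 10 placebo cases: m = 30 and V = 200·200·30·370 / (400²·399) = 6.955. The statistic is (5 − 0.5)² / 6.955 = 2.91 (p = 0.088). Futility is not declared.

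**Step 3: probability that the rule is met.** Exact binomial enumeration at 200 per arm, placebo 5%, continuity corrected. The signed rule uses Z, the square root of the corrected chi-square, positive when NTZ has fewer cases; √0.179 = 0.423 and √0.958 = 0.979.

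| NTZ rate | Unsigned, χ² < 0.179 | Signed, Z < 0.423 | Unsigned, χ² < 0.958 | Signed, Z < 0.979 |
|---|---|---|---|---|
| 1% (design) | 4.3% | 4.4% | 11.9% | 11.9% |
| 5% (no effect) | 46.0% | 73.0% | 76.7% | 88.3% |
| 7.5% | 29.3% | 95.2% | 53.8% | 98.6% |
| 10% | 9.4% | 99.5% | 22.0% | 99.9% |
| 15% | 0.2% | about 100% | 1.1% | about 100% |

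The unsigned columns peak at no effect and fall as NTZ does worse; the signed columns rise throughout. Simulation with 20 LTCFs of 10 per arm (200,000 trials per scenario) agrees within 1 percentage point. Without the continuity correction, the χ² < 0.179 rule is met in 30.6% (no effect), 20.3%, 6.2% and 0.1% (15%), which is the same pattern.

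**The case against.** **Harm is the task of the safety review.** The 50% look is also a safety review, and its unblinding conditions include the COVID-19 rate and safety considerations. SAP 2.4 adds an IDMC review of safety and efficacy at 25 laboratory-confirmed cases. Among these 400 subjects, 25 symptomatic cases would be reached with probability 53%, 85% and 99.7% at NTZ rates of 7.5%, 10% and 15%. This stands. A reader might infer from the table that about 90% of trials with a doubled COVID-19 rate would run on. The documents do not support that: the table describes one criterion, not whether the trial stops. Equally, they print no harm boundary for COVID-19, and the charter is not among them, so this protection can be neither confirmed nor ruled out.

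**Adverse events.** Protocol section 10 says symptoms and "complications of VRIs will not be reported as adverse events", so a reader might infer that safety data offer no backstop. That goes too far. Protocol 10.2 requires serious events and deaths from any cause to be reported at once, SAP 6.3 tabulates deaths by arm, and COVID-19 hospitalization and mortality are secondary endpoints. What stands is that routine adverse-event tables would largely miss excess non-serious COVID-19 illness.

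**An unsigned bound can be deliberate.** With a two-sided alternative, stopping only when |Z| is small (an inner wedge) is a recognised group-sequential form. But neither document says that this is the design, and rejecting the null in the direction of harm would not answer the stated objective, which is prevention.

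**A one-sided p-value would already be directional.** This is true, but the plan's test is two-sided, and Step 1 shows that 0.179 and a one-sided 0.3278 do not match.

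**Conclusion.** The point holds for the rule as written, under either 0.179 or the printed p-value read as two-sided, and with or without the continuity correction. At the 0.179 bound, the unsigned rule is met in 46% of null trials against 73% for a signed rule, a gap of 27 percentage points. At an illustrative NTZ rate of 10% the figures are 9% and 99.5%. The falling pattern applies from equal rates upwards. The sizes assume 200 per arm, a placebo rate of 5% and an unblinded look that takes place.

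This should be fixed, but it is a limited defect: it affects the futility criterion, not type I error, and it does not show that the trial would continue in the face of harm.

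**What to change.** In SAP 2.4 and the IDMC charter, define a signed stratified statistic, Z = (expected − observed NTZ cases) / √(CMH variance), summed over LTCFs and positive when NTZ has fewer cases. Say whether the 0.5 continuity correction is applied to the absolute difference before the sign is restored. Conclude futility when Z is below one positive bound, so that any result with NTZ at or above its expected count meets the criterion.

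State that bound once, on the Z scale, with its matching p-value. Keeping chi-square 0.179 means Z = 0.423 (two-sided p = 0.672). Keeping p = 0.3278 two-sided means Z = 0.979 (chi-square 0.958).

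The cost is a short text change in two documents. Adding a futility stop cannot inflate type I error. At the design effect, making the 0.179 bound signed changes stopping from 4.3% to 4.4%, a negligible loss of power. Choosing the 0.958 bound stops about 12% of trials at the design effect, signed or unsigned, so that choice needs a deliberate decision.
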